1 PROTOCOL SUMMARY

1.1 SYNOPSIS

Title: Effects of Exercise on Glymphatic Functioning and Neurobehavioral

Correlates in Parkinson's Disease

Study Description: This study will assess patients with a clinical diagnosis of Parkinson's

disease (PD) over prior and following participation in a 12-week community-based exercise program, assessing neuroimaging (beta-amyloid deposition, glymphatic flow), and clinical severity (motor,

cognitive, sleep disturbance, mood).

Objectives: Primary Objective:

Evaluate the glymphatic functioning and beta-amyloid burden response to

12 weeks of a community-based exercise course in PD patients.

Secondary Objectives:

Quantify the association between glymphatic functioning, beta-amyloid

burden, and neurobehavioral dysfunction in PD.

Evaluate the degree to which neuroimaging-based response to exercise

mediates clinical improvement in PD.

Tertiary Objectives:

Evaluate whether the association between glymphatic functioning, betaamyloid burden, and neurobehavioral dysfunction in PD differs between

cognitively healthy and cognitively impaired PD phenotypes.

Evaluate whether the neuroimaging and clinical response to exercise differs between cognitively healthy and cognitively impaired PD

phenotypes.

Quaternary Objectives:

Develop a normative reference group for the Brief Estimate of Seconds Test (BEST) to facilitate PD score interpretation and establish how PD-related neurodegeneration affects time perception. In addition, determine how BEST scores correlate with disease severity, neuroanatomical ROIs, and neuropsychometric cognitive data collected in the previous objectives.

Endpoints: Primary Endpoints:

Glymphatic flow (DTI-ALPS score)
PET/CT (cortical:cerebellar SUVr ratio)

Secondary Endpoints (also used for Tertiary Endpoints):
Unified Parkinson's Disease Rating Scale III (UPDRS-3)

Actigraphy Mini-BEST-est

Freezing Gait Questionnaire

6-minute Walk Tesdt

Hopkins Verbal Learning Test-Revised (HVLT)

Trail Making Test – A & B (TMT)

Stroop Test (Stroop)

Letter Fluency (FAS) Simon Task (Simon)

PROMIS – Sleep Disturbance short forms (PROMIS-Sleep)

Hospital Anxiety and Depression Scale (HADS)

Tertiary Endpoints:

Clinical Dementia Rating Scale (CDR) Brief Estimate of Seconds Test (BEST)

Quaternary Endpoints:

Brief Estimate of Seconds Test (BEST)

Study Population: PD cohort: Patients with a clinical diagnosis of Parkinson's, as defined by

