1 STATISTICAL PLAN

1.1 AIM 1

Aim (1). To quantify the relationship between CNS lymphatic measures and beta-amyloid burden.

- Hypothesis (1A). Glymphatic flow and lymphatic collector velocity inversely correlate with beta amyloid measured from 18F-florbetapir PET in older adults with Parkinson's disease.
- Exploratory Hypothesis (1B). In Parkinson's subjects matched for age and sex, glymphatic flow and betaamyloid burden will be worse in patients with versus without mild cognitive impairment (MCI).

A.1.1 Experiment. We will enroll participants with idiopathic Parkinson's disease (n=32; age range=55- 80 years), equally distributed and matched for age and sex between groups with (n=16) and without (n=16) mild cognitive impairment. These populations provide a cohort to evaluate the potential relationship between glymphatic flow and beta-amyloid burden, given the elevated risk of beta-amyloid accumulation associated with both conditions. These patients will form a cohort to be assessed before and after a community-based exercise intervention. Participants will be recruited from Vanderbilt University Medical Center Neurology's Behavioral and Cognitive and Movement Disorder Clinics by Drs. [name] and [name]. Potential participants will undergo a neurological and neuropsychological examination to characterize their medical and neurobehavioral status. Patients will have medical and motor presentation indicated for the community-based exercise program. Those patients with clinically-defined MCI, will be without evidence of vascular cognitive impairment, primary mood disorder, Lewy body disease, or comorbid medical condition that could contribute to cognitive symptoms (e.g. pulmonary, hematologic, metabolic, or vitamin deficiency).

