Exploratory Hypothesis (2A). Exercise treatment will result in improved glymphatic functioning. Exploratory Hypothesis (2B). Exercise treatment will result in a reduction of cortical beta-amyloid uptake. Exploratory Hypothesis (2C). The degree of improvements in glymphatic functioning and cortical beta-amyloid uptake in response to exercise therapy will be more significant in MCI versus non-MCI participants. D.2.1 Experiment. We will enroll the patients from Aim (1) (A.1.) all of whom are undergoing community-based exercise intervention to treat symptoms of Parkinson's.

A.2.1.1. Exercise intervention procedure. Following baseline assessment, all patients will participate in a community-based kick boxing group exercise class designed for those living with Parkinson's called "Rock Steady Boxing." Patients will complete 12 consecutive, 90-minute, once-weekly classes, then undergo follow-up assessment. Treatment compliance will be monitored by the collaborating exercise trainer. All participants, regardless of degree of treatment compliance will receive follow-up assessment. *A.2.1.2. Imaging procedure.* PET and MRI methods as outlined in A.1.1.2. and A.1.1.3. will be performed.

A.2.2. Analysis and statistical plan. Our main hypotheses are that after 12 weeks of once-weekly exercise treatment for PD, glymphatic functioning (per DTI-ALPS) will improve and beta-amyloid burden (per PET) will decline. We expect that degree of treatment compliance standards will moderate these changes. We will also explore whether scalar degree of treatment compliance relates to degree of change in our assessment modalities. Statistical analysis will be overseen by statistics Co-I [name] and the same considerations outlined in Aims (1) will be applied. To test Exploratory Hypothesis (2A), a paired Student's t-test or Wilcoxon signed-rank test, depending on normality findings, will be applied to determine if glymphatic flow (DTI-ALPS score) is increased after, relative to before, exercise intervention. To test Exploratory Hypothesis (2B), an identical

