procedure will be applied to evaluate differences in SUVr pre vs. post exercise intervention and corrected pvalues will be reported. To gain additional information, a multiple linear regression will be performed using the change in glymphatic flow (DTI-ALPS score) as the dependent variable and degree of compliance and change in beta-amyloid burden as the independent variables. To test Exploratory Hypothesis (2C), we will perform these same comparisons separately for MCI and non-MCI subgroups. Aim 2 hypotheses are exploratory, given limited extant literature defining reliable effect sizes; however, one randomized study (n = 33) demonstrated a 30% divergence in mean plasma levels of a CSF beta-amyloid marker between exercise (-6%) and non-exercise participants (+24%) with MCI. Thus, with the proposed sample size of 32 (each with a measurement before and after intervention), we should have at least 80% power to detect a significant difference in mean DTI-ALPS score pre- vs. post-exercise with at least 80% power and two-sided Type I error=5%. We should also have sufficient power to include two independent variables in the regression model. *A.2.3. Impact.* Results will provide evidence of how CNS lymphatic and beta-amyloid properties adjust in response to regular vigorous exercise in a PD sample.

A.3. Aim (3). Evaluate the degree to which neuroimaging-based response to exercise mediates clinical improvement in neurocognitive functioning and neuropsychiatric symptomatology.

Hypothesis 3.A. Neurocognitive functioning will improve following completion of the exercise intervention. Exploratory Hypothesis (3.B.). Sleep disturbance symptoms will diminish following completion of the exercise intervention.

Exploratory Hypothesis (3.C.). The degree of change glymphatic function and cortical beta-amyloid uptake in response to exercise therapy will be correlated with the degree of improvements in neurocognitive functioning.

Exploratory Hypothesis (3.D.). The degree of change glymphatic function and cortical beta-amyloid uptake in response to exercise therapy will be correlated with the degree of improvements in sleep disturbance symptomatology.

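### The DTI-ALPS and SUVr response to exercise is primary in the protocol but labelled exploratory in the SAP, and the stated 80% power for the DTI-ALPS change has no DTI-ALPS input behind it

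*SAP*

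**What the plan says.** **Protocol.** In section 1.1 (Synopsis) the primary objective begins "Evaluate the glymphatic functioning and beta-amyloid burden response to" a 12-week exercise course, and the primary endpoints are DTI-ALPS and the cortical:cerebellar SUVr ratio. A secondary objective begins "Quantify the association between glymphatic functioning, beta-amyloid" burden and neurobehavioural dysfunction. The cognitive tests are secondary endpoints. Section 2.1 enrols 50 participants with Parkinson's disease.

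**SAP, status of the hypotheses.** Aim 2 lists the DTI-ALPS response (2A) and the SUVr response (2B) as exploratory. The analysis text keeps that label: "To test Exploratory Hypothesis (2A), a paired Student's t-test or Wilcoxon signed-rank test, depending on normality findings, will be applied to determine" whether DTI-ALPS has risen. It then gives a reason: "Aim 2 hypotheses are exploratory, given limited extant literature defining reliable effect sizes". The same section (A.2.2) nevertheless opens by presenting these two expectations as the main hypotheses. Only two hypotheses in the SAP lack the exploratory label. One is 1A, "Glymphatic flow and lymphatic collector velocity inversely correlate with beta amyloid" on PET. The other is 3A, "Neurocognitive functioning will improve following completion of the exercise intervention".

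**SAP, power and sample size.** A.2.2 cites a randomised study of 33 people that "demonstrated a 30% divergence in mean plasma levels of a CSF beta-amyloid marker between exercise (-6%) and non-exercise participants (+24%) with MCI". From this it concludes that with 32 participants, each measured before and after, "we should have at least 80% power to detect a significant difference in mean DTI-ALPS score pre- vs. post-exercise" at a two-sided 5% level. A.1.1 words the 32 as the number to be enrolled. Section B says a possible 10% attrition or exclusion has been accounted for.

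**The concern.** A trial's primary question has to be fixed before its results are known. Here the protocol and the SAP give the same two tests different standing, and the SAP's own wording points both ways. A favourable pre/post result could be presented as the primary finding and an unfavourable one as exploratory, each with a document to cite. Whether DTI-ALPS and SUVr need a multiplicity rule depends on the same unsettled choice.

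The power sentence adds to this. It reads as a calculation for one of the protocol's primary endpoints, but the section first says reliable effect sizes are lacking and then draws the 80% from a different measure, in a different population, under a different design. The other primary endpoint has no power statement. The sample size behind the sentence is also unsettled, both between the documents and against the SAP's own attrition allowance.

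**Working it through.** **1. Status, side by side**

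| Question | Protocol 1.1 | SAP |
|---|---|---|
| DTI-ALPS change with exercise | Primary objective and endpoint | 2A: exploratory, also called main |
| SUVr change with exercise | Primary objective and endpoint | 2B: exploratory, also called main |
| DTI-ALPS and SUVr correlation | Part of a secondary objective | 1A: no exploratory label |
| Cognitive improvement | Secondary endpoints | 3A: no exploratory label |

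**2. A check on method: the SAP's 1A power**

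Inputs from A.1.3 are |r| = 0.49, n = 32, two-sided 5%. With Fisher's z, power = Φ(atanh(0.49)·√(n−3) − 1.96).
- n = 32: Φ(0.536 × 5.385 − 1.96) = Φ(0.927) = 82.3%. The SAP's 82% is reproduced.
- n = 29: Φ(0.536 × 5.099 − 1.96) = Φ(0.773) = 78.0%.

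**3. The Aim 2 power**

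A paired t-test needs dz = mean change / SD of change. The SAP gives n = 32, two-sided 5% and 80%, but no mean change, SD of change or pre/post correlation for DTI-ALPS. The 80% therefore cannot be reproduced. It can only be solved backwards.

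Power = P(|T| > t(n−1; 0.975)), where T is noncentral t with n − 1 degrees of freedom and noncentrality dz·√n. The normal approximation for 32 pairs is (1.960 + 0.842)/√32 = 0.495; the exact value is 0.511.

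Completers after 10% loss: 32 × 0.9 = 28.8, taken as 29; 50 × 0.9 = 45.

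| Pairs analysed | dz for 80% power, two-sided 5% | Same, two-sided 2.5% (only if alpha is split over two endpoints) |
|---|---|---|
| 32 | 0.51 | 0.57 |
| 29 (from 32 enrolled) | 0.54 | 0.60 |
| 50 | 0.40 | 0.45 |
| 45 (from 50 enrolled) | 0.43 | 0.47 |

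Power at two-sided 5% over an assumed range of dz (the true value is unknown):

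| dz | 29 pairs | 32 pairs | 45 pairs | 50 pairs |
|---|---|---|---|---|
| 0.3 | 34.5% | 37.6% | 50.3% | 54.8% |
| 0.4 | 54.8% | 59.2% | 74.7% | 79.2% |
| 0.5 | 73.9% | 78.2% | 90.7% | 93.4% |
| 0.6 | 87.7% | 90.8% | 97.6% | 98.6% |

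**4. Can the plasma contrast supply dz?**

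The divergence is 24 − (−6) = 30 points, of which 24 come from the non-exercise arm. This study has one cohort and no such arm. The within-exercise part is 6 points. Even if plasma points could stand in for DTI-ALPS, 80% power with 32 pairs would need an SD of change of at most 6/0.511 = 11.7 points. Using all 30 points, the SD could be as large as 30/0.511 = 58.7. No SD is given, so the contrast fixes nothing.

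**5. Other DTI-ALPS figures in the SAP**

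A.1.3 gives d = 2.3 between people with and without MCI, and the correlation of −0.49 with SUVr. Both are cross-sectional. Neither gives an SD of change.

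**6. Attrition**

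The SAP enrols 32 and powers on 32 complete pairs, which leaves no room for 10% loss. To end with 32 pairs it would need 32/0.9 = 35.6, so 36 enrolled.

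**The case against.** The best defence is that the SAP uses the word exploratory mainly to describe a thin evidence base. It gives that reason itself, never ranks its hypotheses as primary or secondary, calls 2A and 2B its main hypotheses, and in A.3.2 uses main and exploratory together. A reader might infer from the labels that the two documents have simply swapped primary and secondary. The SAP does not support so clean a reversal. What stands is that its explicit label conflicts with the protocol and sits badly with its own wording.

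On power, a reader might infer that the 80% is wrong or the study underpowered. That is not shown: with dz of 0.51 or more the statement is true for 32 pairs. The detectable standardised change can also be worked out from n, alpha, test and power, so only the change in DTI-ALPS units is out of reach. And if the protocol's 50 governs, 45 completers exceed 32 and the claim becomes easier to meet.

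A reader might also take the missing SUVr power to contradict SAP section D. It does not: section D promises power calculations for each aim, and Aim 2 has one, for DTI-ALPS. The SUVr gap stands only because SUVr is a primary endpoint in the protocol.

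The protocol describes the study as observational and names a single site. That lowers the stakes, but the protocol still names a primary objective and endpoints.

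**Conclusion.** The point holds on two counts.

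**Status.** This must be settled. The protocol's primary objective and both primary endpoints are explicitly exploratory in the SAP, which also calls them main. Nothing in either document decides between the two before results are seen.

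**Power.** This should be corrected. The 80% for the DTI-ALPS change is unsupported rather than refuted. It requires dz of at least 0.51 with 32 complete pairs. After the 10% loss, the detectable dz is 0.54 (29 pairs) or 0.43 (45 pairs). At 29 pairs the 82% for 1A becomes 78%. SUVr change has no power statement.

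Both sample sizes are worded as enrolment. The problem is therefore a mismatch between enrolment, complete pairs and the stated attrition allowance, and not doubt about whether 32 or 50 already excludes dropouts.

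The figures assume a two-sided paired t-test with normally distributed changes. The SAP's signed-rank alternative needs slightly more under normality (0.511/√0.955, about 0.52 at 32 pairs). The dz range is an assumption. The SAP's claim in section C to be powered for sex differences is a separate matter and is not judged here.

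**What to change.** 1. **Status.** In a dated amendment made before any pre/post results are seen, or stating that some have been, give 2A and 2B one status in both documents and align the main-hypotheses line in A.2.2 with it.
   - If primary: state whether either endpoint or both must succeed, and name a multiplicity rule if either suffices.
   - If exploratory: reword the protocol's primary objective and endpoints.

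2. **Power.** Delete the inference from the plasma marker. Replace the 80% claim with text such as: *With N completers, a paired t-test at two-sided 5% has 80% power for a mean DTI-ALPS change of dz SDs of the within-person change; the SD of change is [value and source], or is not available.* Use dz = 0.54 (29 pairs from 32 enrolled) or 0.43 (45 pairs from 50), or 0.60 and 0.47 if alpha is split over the two endpoints. SAP sections B and D mention DTI-ALPS data in 61 older subjects and reproducibility work, which may yield an SD. Make the same statement for SUVr once the PET tracer is reconciled: protocol 2.2 names C11PiB, while SAP Hypothesis 1A and A.1.1.2 name florbetapir.

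3. **Sample size.** Reconcile 32 with 50, and base every power statement, including that for 1A, on completers.

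**Cost.** Items 1 and 2 are text changes in both documents and need no extra participants. Requiring either endpoint, with alpha split, raises the detectable dz (0.54 to 0.60 at 29 pairs). Requiring both costs no alpha but lowers the chance of overall success. Choosing exploratory means the protocol needs another primary objective. Item 3 may not be free: the two enrolment figures differ by 50 − 32 = 18 participants, each with two MRI and two PET scans.

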| Vital Signs/orthostatic blood pressure/ weight | | х | | | | |
| Blood sample | | х | | | | х |
| Neurologic exam | | х | | | | х |
| UPDRS-3 | X (on-med) | X (off- med | | | | х |
| Neuropsychological exam (all cognitive measures) | | х | | | | х |
| Questionnaires (sleep, mood) | | Х | | | | х |
| Actigraphy | | X | | | | x |
| MRI Brain | | х | | | | Х |
| PET/CT Brain | | х | | | | х |
| Physical status assessment (Mini-BESTest, Freezing Gait Questionaire, 6-minute Walk Test) | | | х | | х | |

VUMC = Vanderbilt University Medical Center site

RSB = Rock Steady Boxing site

The Healthy cohort will complete only a single visit, for 10 minutes, in which they will complete the informed consent and the BEST, as well as asked about demographics, medical history, and exclusion/inclusion criteria.

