2.2 STUDY DESIGN SPECIFICS

Clinical Assessments

PD cohort

All potential participants will undergo neurological and neuropsychological examination to determine eligibility, categorize MCI status, and provide quantification of neurocognitive functioning and neuropsychiatric symptomatology.

Screening data (see inclusion/exclusion criteria) from eligible enrollees will be also used as part of clinical baseline assessment.

Neurological examination will include the Unified Parkinson's Disease Rating Scale III (UPDRS-III)⁵⁶ and the Clinical Dementia Rating (CDR)⁵⁷ scale. Vitals and a blood sample (10mL) will be collected as part of this examination. Medical history will include an inquiry as to whether the participant is actively dieting.

The neuropsychological examination protocol will consist of a memory measure (i.e., the Hopkins Verbal Learning Test – Revised [HVLT-R]⁵⁸, consisting of Learning, Recall, and Recognition subcomponents), executive functioning measures (i.e., Trail Making Test – A & B⁵⁹, Verbal Fluency [FAS]⁶⁰, Stroop⁶¹), and exploratory measures of cognitive-performance thought potentially sensitive to PD-related pathology (Brief Estimate of Seconds Test [BEST]⁶², Simon Task⁶³). To evaluate sleep disturbance symptomatology,

PROMIS – Sleep Disturbance (SD) and Sleep-related Impairment (SRI) short forms will be administered⁶⁴. To evaluate mood symptomatology, the Hospital Anxiety and Depression Scale (HADS)⁶⁵ will be administered.

Physical assessment is routinely completed at the first and last visit of the community-based exercise program, including rating/timing of ability to complete simple posture and gait tasks, as well as self-reported difficulty with gait initiation. UPDRS-III will also be administered at screening (on-drug), baseline assessment (off-drug), and follow-up assessment (off-drug) Additionally, between enrollment and competition, the patients will wear an actigraph to continuously measure motor activity.

Healthy cohort:

All participants will be administered the Brief Estimate of Seconds Test (BEST) in person or via Microsoft Teams.

Imaging

PD cohort

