A.1.1.1. Clinical and neuropsychological examination. All potential participants will undergo baseline clinical and neuropsychological examination to determine eligibility, categorize MCI status, and provide quantification of neurocognitive functioning and neuropsychiatric symptomatology. The neuropsychological examination protocol will consist of memory measure (i.e., the Hopkins Verbal Learning Test – Revised [HVLT-R], consisting of Learning, Recall, and Recognition subcomponents). We will also administer three executive functioning measures (i.e., Trail Making Test – A & B57, Verbal Fluency [FAS], Stroop]), to facilitate exploratory analyses. To evaluate sleep disturbance symptomatology, PROMIS – Sleep Disturbance (SD) and Sleep-related Impairment (SRI) short forms will be administered.

A.1.1.2. PET. A single administration of approximately 370 MBq (10 mCi) Florbetapir 18F, then a 10- minute PET acquisition (2 × 5 minute frames) approximately 50 minutes later will be performed. Images will be reconstructed using an ordered subset estimation algorithm (4 iterations, 16 subsets, with a post-reconstruction Gaussian filter of 5 mm), and corrected for scatter and attenuation. Images will be co-registered to the high spatial resolution T1-weighted image as we have performed previously and a mean cortical:cerebellar SUVr will be calculated as the primary parameter of interest. For exploratory evaluation, we will also record SUVr in bi-temporal, bi-occipital, bi-frontal, and biparietal lobes.

A.1.1.3. MRI. The following imaging and angiography sequences will be completed. We will apply our previously reported 3T methods (16-channel neurovascular coil) with the below 50 min protocol:

Anatomical imaging. T1-weighted (MPRAGE; spatial resolution=1.0x1.0x1.0mm3; 3D turbo-gradient-echo; TR/TE=8.2/3.7ms), and T2-weighted (FLAIR; spatial resolution=0.9x1.1x3.0mm3; turbo-inversion-recovery; TR/TI/TE=11000/2800/120ms) imaging, and intracranial (spatial resolution = 0.5x0.8x1.4mm3; 3D gradient

echo; TR/TE=23/3.5ms) and extracranial (spatial resolution=0.9x0.9x3.0mm3 ; 2D gradient echo; TR/TE=18.6/3.2ms) time-of-flight (TOF) MR angiography (MRA).

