Spin labeling for cervical LN perfusion. Spin labeling will be performed with an 11-ms hypersecant inversion (labeling) prepulse, followed by an inversion time range of 300 to 2400 ms in 300 ms increments, which will enable blood transit time and perfusion quantification. Other parameters: labeling=STAR; TE=11 ms; spatial resolution=2x2x2 mm3; averages=14.

A.1.2. Analysis and statistical plan.

A.1.2.1 Clinical and neuropsychological examination. MCI will be defined based on established clinical criterion of cognitive performance below 1.5 standard deviations compared to age-based normative expectations in the memory domain and/or the executive functioning domain, with a Clinical Dementia Rating (CDR) of 0 or 0.5, indicating cognitive dysfunction has not contributed to functional dependence for activities of daily living61, 62. The memory domain by determining the mean memory score across performance on the HVLT-R (i.e., Learning Trials 1- 3, Delayed Recall, Delayed Recognition). Similarly, an executive functioning domain will be determined by the mean score across the TMT (part B), Stroop, and Letter Fluency. Clinical analyses will be overseen by Drs. [name] and [name].

A.1.2.2. Image analysis. Analysis will be overseen by the PI and radiology Co-Is Drs. [name] and [name], who together have experience with all image types. Lymphatic spin labeling. Sequential images are acquired (A) without and (B) with magnetic labeling (adiabatic inversion of arterial water spins). Following labeling, blood water flows into LNs (C,D) and attenuates signal. The difference image is proportional to perfusion

(ml/100g/min), which can be quantified upon application of the flow modified Bloch equation (E: T2-weighted image of LNs; F: corresponding perfusion weighted signal). (G) The blood arrival (red) and lymph arrival (black) following labeling over six subjects and LNs (dimensions shown above). The blood signal peaks and decays first, with the magnitude indicating perfusion. The lymph signal peaks later, due to slower lymphatic flow; note that the lymphatic signal is detectable at such long delays due to the longer T1 of lymph (T1=3100 ms) relative to blood (T1=1650 ms).

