A.3.1. Experiment. We will enroll the patients from Aim 2 all of whom completed the community-based exercise intervention and underwent pre/post neuroimaging protocols. • Neuropsychological examination. Subjects will undergo follow-up neuropsychological examination to quantify neurocognitive functioning and neuropsychiatric symptomatology. The neuropsychological examination protocol will be the same outlined in A.1.1.1.

A.3.2. Analysis and statistical plan. Our main exploratory hypothesis is that the degree of improvement in glymphatic functioning (per DTI-ALPS) and decreased beta-amyloid burden (per PET) will significantly associate with neurobehavioral dysfunction improvements. We will also explore whether scalar degree of treatment compliance relates to degree of change in our assessment modalities. Statistical analysis will be overseen by statistics Co-I [name] and the same considerations outlined in Aims (1) will be applied. To test Hypothesis (3A) a paired Student's t-test or Wilcoxon signed-rank test, depending on normality findings, will be applied to determine if memory and executive functioning domain averages are improved after, relative to before, exercise intervention. We have powered this aim based on recent literature that has shown a medium improvement in executive functioning in between subject design (spatial working memory task, np2 = 0.17; MoCA global cognitive screen, np2 = 0.133; Treatment n = 24, Control n = 9) and large effect size withinsubject design (TMT-B-A time, np2's = 0.34; n = 19)70. To test Exploratory Hypothesis (3B), a paired Student's t-test or Wilcoxon signed-rank test, depending on normality findings, will be applied to determine if PROMIS – SRI and SD symptom scores are reduced is after, relative to before, exercise intervention. To test Exploratory Hypothesis (3C), two multivariate linear regressions will be employed, both will enter mean memory and

mean executive functioning domain scores as independent variables, with one regression using DTI-ALPS score and the other using cortical:cerebellar SUVr ratio as sole dependent variables. Exploratory Hypothesis (3D) analysis will be the same, with PROMIS – SRI and SD symptom scores substituted as independent variables. *A.3.3. Impact.* Results will provide evidence of how CNS lymphatic and beta-amyloid burden response to regular vigorous exercise in a PD sample relates to neurobehavioral functioning, as a clinical outcome metric.

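### Hypothesis 3A is an uncontrolled retest of the scores that classify MCI, so practice gain, and in the MCI half regression to the mean, can pass as exercise benefit

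*SAP*

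**What the plan says.** - **Hypothesis.** SAP, Aim 3, Hypothesis 3A: "Neurocognitive functioning will improve following completion of the exercise intervention". Hypotheses 3B to 3D are labelled exploratory; 3A is not.
- **Test.** SAP A.3.2: a paired t-test or Wilcoxon signed-rank test "will be applied to determine if memory and executive functioning domain averages are improved after, relative to before, exercise intervention".
- **MCI rule.** SAP A.1.2.1: "cognitive performance below 1.5 standard deviations compared to age-based normative expectations in the memory domain and/or the executive functioning domain", together with a CDR of 0 or 0.5. Memory is "the mean memory score across performance on the HVLT-R"; executive functioning is "the mean score across the TMT (part B), Stroop, and Letter Fluency". These are the two domain averages that 3A tests.
- **One examination, two uses.** SAP A.1.1.1: all potential participants "will undergo baseline clinical and neuropsychological examination to determine eligibility, categorize MCI status, and provide quantification of neurocognitive functioning". Protocol 2.2 agrees that screening data "from eligible enrollees will be also used as part of clinical baseline assessment". The Protocol's schedule of activities shows one cognitive examination before exercise (Day 1-7) and one after (Day 92-99).
- **Follow-up.** SAP A.3.1 repeats the A.1.1.1 protocol and is silent on alternate forms.
- **Composition.** MCI and non-MCI are enrolled 1:1: 16 and 16 in the SAP, 25 and 25 in the Protocol.
- **Comparator.** All PD patients exercise. The healthy cohort takes only the BEST, once.
- **Nearest safeguard.** SAP A.3.2 plans to explore whether compliance relates to change, but not as part of the 3A test.

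The SAP's limitations section mentions neither practice nor regression to the mean.

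**The concern.** A paired test against zero asks only whether scores rose. Two things can raise them without exercise. Repeating the same tests can bring practice gain, in MCI and non-MCI patients alike. Separately, patients placed in the MCI group because an error-prone score fell below a cut-off tend to score higher on retest. Age-based norms place a score at one sitting and remove neither effect.

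At stake is what 3A can support. The SAP describes Aim 3 results as a response to regular vigorous exercise, and the aim itself speaks of clinical improvement. The Protocol's tertiary objective then compares clinical response between cognitively impaired and cognitively healthy patients. There the selection artefact favours the impaired group.

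**Working it through.** **The plan's own figures.** The SAP gives no sample size, power or SD of change specific to 3A. Its reproducible power figure for n=32 is Aim 1's 82% for a correlation of -0.49: Φ(atanh(0.49)·√29 − 1.96) = Φ(0.536 × 5.385 − 1.96) = Φ(0.93) = 82.3%, which agrees. For 3A it cites a within-subject partial eta-squared of 0.34 with n=19. Read as a one-degree-of-freedom effect, F = (0.34/0.66) × 18 = 9.27 and dz = √(9.27/19) = 0.70. A paired test would then have 97% power at n=32. The smallest dz detectable with 80% power is 0.51 at n=32 and 0.40 at n=50.

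**Retest interval.** 92 − 7 = 85 days to 99 − 1 = 98 days, about 12 to 14 weeks.

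**Assumptions not in the documents.** Retest reliability 0.7 to 0.9. Source-population mean 0, −0.5 or −1.0 SD against norms, which implies about 12%, 26% or 47% MCI. True-score correlation between domains 0.5. Practice gain 0, 0.1 or 0.2 SD. The true exercise effect is set to zero. The rate counted is significant improvement at two-sided 5%, so nominal is 2.5% per domain and about 5% for either domain.

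**Step 1: practice alone.** With unit score SD, the SD of change is √(2(1 − reliability)), and dz is the practice gain divided by it. Example: gain 0.2, reliability 0.8, dz = 0.2/0.632 = 0.32. The noncentral t then gives 41% at n=32.

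| Practice gain | n=32, reliability 0.7 / 0.8 / 0.9 | n=50, reliability 0.7 / 0.8 / 0.9 |
|---|---|---|
| 0.1 SD | 11% / 14% / 23% | 14% / 19% / 34% |
| 0.2 SD | 29% / 41% / 69% | 43% / 59% / 87% |

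**Step 2: regression to the mean alone.** This was simulated with MCI assigned if either observed baseline domain is below −1.5, 1:1 enrolment, and the classifying score used as baseline. At reliability 0.8:

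| MCI share of source | MCI half | Non-MCI half | Pooled 1:1 |
|---|---|---|---|
| 12% | +0.180 SD | −0.023 SD | (0.180 − 0.023)/2 ≈ +0.08 SD |
| 26% | +0.136 SD | −0.050 SD | (0.136 − 0.050)/2 ≈ +0.04 SD |
| 47% | +0.095 SD | −0.083 SD | (0.095 − 0.083)/2 ≈ +0.01 SD |

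The two halves cancel when weighted by their share of the source: 0.118 × 0.180 − 0.882 × 0.023 ≈ 0.001. The pooled bias therefore comes only from the 1:1 quota over-representing MCI.

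False improvement at n=32 over the reliability range:

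- Pooled, per domain: 7-12% at 12% MCI, 4-7% at 26%, and 2.5-2.7% at 47%.
- Pooled, either domain: up to 23%.
- MCI half only, per domain: 6-25%, with a spurious gain of 0.05-0.28 SD.
- MCI appearing to gain more than non-MCI: about 8-19% per domain, against 2.5%.

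**Step 3: both together.** Pooled per domain at n=32: 11-39% with 0.1 SD practice and 31-82% with 0.2 SD. With 0.2 SD and reliability 0.8, at least one domain is falsely positive in 68-89% of trials at n=32 and 86-98% at n=50. The larger sample makes the error more likely.

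**Step 4: can attendance separate exercise from artefact?** Change in a domain was regressed on attendance and baseline score, with no exercise effect. If attendance is unrelated to cognition, false benefit stays near 2.5%. If attendance correlates 0.3 with true cognition (assumed), it is about 5-9% at n=32 and 5-13% at n=50, because an error-prone baseline adjusts only in part.

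**The case against.** The strongest reply is that the study is labelled observational, cognition is a secondary endpoint, and readers know that a pre-post change has no control. The label stands. But the SAP states a directional hypothesis for 3A without the exploratory tag, says the aim is powered, and gives no caution about retest.

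Other points stand and limit the concern:

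- A reader might infer that selecting half the sample on low scores by itself makes 3A positive. The documents do not support that. 3A is pooled, the non-MCI half drifts down, and the source share of MCI is not given. Recruitment includes a behavioural and cognitive clinic, so that share may be high.
- A.3.2 specifies no MCI-only test of cognition; the SAP's separate subgroup comparisons (2C) concern imaging. The MCI-half figures therefore bear on the Protocol's tertiary phenotype objective and on any subgroup reading, not on the 3A test itself.
- A reader might infer that the imaging-cognition regressions are invalidated too. 3C tests slopes, and a uniform practice gain moves only the intercept. With imaging change simulated as independent of cognition, its overall test rejected 4.7% of the time against 5%.
- It is tempting to make attendance the main exercise test. Attendance is self-selected: Protocol 2.2 excludes nobody on it, and one class suffices for completion under 2.3. Step 4 shows the result.
- The size of the practice gain comes from no document, and the text does not say that identical test forms will be used.

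**Conclusion.** The concern holds in this form: as written, 3A can declare cognitive improvement after exercise when only retest effects are present, and nothing in the plan separates the two. Practice is the main threat to the pooled test; with an assumed 0.1 to 0.2 SD gain and regression to the mean included, the false-improvement rate per domain is roughly 11-82% at n=32. Regression to the mean alone adds little or nothing if MCI is about half the source, and brings the rate to at most about 12% if MCI is about 12% of it. Its direction is certain only in the MCI half, so it biases the phenotype comparison towards MCI.

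The sizes rest on assumed reliability, practice gain and MCI share. The direction rests on the documents' design. A reader might infer that a positive 3A would be false. The documents do not show that; they show only that such a result could not be attributed to exercise. The SAP should be changed on this point, but no redesign is needed.

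**What to change.** 1. Restate 3A as uncontrolled change over about 12 to 14 weeks that includes practice and regression to the mean, and say that it is not evidence that exercise improves cognition.
2. Use alternate forms at follow-up, in counterbalanced order, for the tests that have them.
3. State that neither an MCI-only gain nor a larger cognitive gain in MCI than in non-MCI will be read as exercise benefit.
4. Keep the planned compliance-change analysis exploratory, adjust it for baseline domain score and age, and state that attendance is self-selected and that the slope cannot replace a control group.

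Items 1, 3 and 4 need SAP wording and covariates already collected. Item 2 needs the forms and a counterbalancing list. The downside is a weaker 3A claim and a little extra variance from differences between forms.

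Stronger remedies cost more. A separate baseline examination after classification returns the regression-to-the-mean error to nominal (2.4-2.7% per domain in simulation) but leaves practice. A concurrent non-exercise group removes both. For a 0.70 SD difference in change it needs 2 × (1.96 + 0.84)²/0.70² ≈ 32.0, so about 33 per arm for 80% power. That would be a different study.
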